1.0 Objectives

1.1 Describe the purpose, specific aims, or objectives of this research.

Response:

Aim 1.1: To compare changes in albuminuria levels (UACR) following 1-year treatment with exenatide-extended release (weekly exenatide) or placebo in T2DM with macro- and microalbuminuria.

Aim 1.2: To evaluate changes in creatinine, creatinine clearance, GFR and cystatin C following 1-year treatment with exenatide-extended release (weekly exenatide) or placebo in T2DM with macro- and microalbuminuria.

Aim 2.1: To evaluate the changes in TGF β levels and in the expression of two major signal transducers of TGF β signaling, SMAD3 and SMAD4 in MNC following 1-year treatment with exenatide-extended release or placebo in T2DM with macro- and microalbuminuria.

Aim 2.2: To investigate the changes in profibrotic genes such as type I and IV collagen, connective tissue growth factor (CTGF), PAI-1, TIMP-1 and 2 and fibronectin (fibronectin EDA) following 1-year treatment with exenatide-extended release or placebo in T2DM with macro- and microalbuminuria.

Aim 3.1: To evaluate the change in reactive oxygen species (ROS) generation and NADPH oxidase subunit (p47^{phox}) in MNC and urinary isoprostanes following 1-year treatment with exenatide-extended release or placebo in T2DM with macro- and microalbuminuria.

Aim 3.2: To investigate the changes in Nrf-2/keap-1 system activation and anti-oxidant response genes including NQO-1, GST-1P and HO-1 expression following 1-year treatment with exenatide-extended release or placebo in T2DM with macro- and microalbuminuria

1.2 State the hypotheses to be tested, if applicable.

NOTE: A hypothesis is a specific, testable prediction about what you expect to happen in your study that corresponds with your above listed objectives.

Response: **Hypothesis 1:** Treatment with weekly exenatide reduces the rate of progression and possibly reverses the rate of albuminuria in patients with type 2 diabetes (T2DM).

Hypothesis 2 (exploratory): Exenatide extended release treatment suppresses TGF- β 1 activation in T2DM with micro and macroalbuminuria.

Hypothesis 3 (exploratory): Exenatide extended release treatment suppresses oxidative stress and induces anti-oxidant mediators in T2DM with micro and macroalbuminuria.

2.0 Scientific Endpoints

2.1 Describe the scientific endpoint(s), the main result or occurrence under study.

NOTE: Scientific endpoints are outcomes defined before the study begins to determine whether the objectives of the study have been met and to draw conclusions from the data. Include primary and secondary endpoints. Some example endpoints are: reduction of symptoms, improvement in quality of life, or survival. Your response should **not** be a date.

Response:

This is a prospective study to evaluate effect of Exenatide extended release treatment for 1 year on albuminuria levels in T2DM patients with micro- and macroalbuminuria compared to placebo. The similarities in baseline values between the study groups will be compared using appropriate parametric tests. Transformations of the data on order to meet statistical assumptions may be considered. All statistical analysis will be carried out using SPSS software (SPSS Inc, Chicago, Illinois) based on intention to treat principle. Data will be presented as mean±standard error. The primary endpoint of the study is the change from baseline in albuminuria level at weeks 12, 26, 39 and 56 following Exenatide extended release and placebo treatments. Fasting samples collected at weeks 0, 12, 26, 39 and 56 will be used for this assessment with values at week 0 considered as baseline. Changes from baselines from both drugs arms will be compared to those from the placebo arms in both the micro and macroalbuminuria groups. The statistical analysis will be done using mixed model for repeated measurement (MMRM) analysis with assigned α value of 0.05. Our preliminary data on retrospective analysis of the difference in albuminuria following GLP-1RA treatment for 2.5 yrs in T2DM patients with micro and macroalbuminuria show regression of albuminuria (UACR) by approximately 55mg/mg and 500mg/g (about 50% reduction), respectively. Conservatively estimating a difference in the change from baseline in albuminuria after 1 year between the Exenatide extended release and placebo groups (across both albuminuria groups) of 60mg/g, with standard deviation of no more than 91mg/g, a sample size of 38 patients per group should provide adequate power ($\beta = 0.2$) to detect a significant difference ($\alpha = 0.05$). Assuming a drop-out rate of 15% and 2:1 drug:placebo randomization ratio, 60 active and 30 control will be recruited for a total of 90 patients (rounded up). Patients will be enrolled based on a predetermined stratification according to the two albuminuria categories (micro and macro at 1:1 ratio) with 45 patients in each.

The secondary end points include the comparison of the changes in albuminuria based on baseline albuminuria category (micro or macro), creatinine clearance, Cystatin C, TGF β , type I and IV collagen, CTGF, and fibronectin levels, the expression of SMAD3, SMAD4, NQO-1, GST-1P and HO-1, Nrf-2/keap-1 system activation between the Exenatide extended release and placebo groups and across albuminuria categories.

3.0 Background

3.1 Provide the scientific or scholarly background, rationale, and significance of the research based on the existing literature and how it will contribute to existing knowledge. Describe any gaps in current knowledge. Include relevant preliminary findings or prior research by the investigator.

Response:

Diabetic nephropathy is the leading cause of chronic kidney disease accounting for nearly 50% of all end-stage renal disease worldwide (1). Current therapies that aim to lower blood glucose are not effective in blocking renal damage, and cotreatment with renoprotective drugs often results in toxicity, limiting efficacy. Hence, there remains an urgent need to develop effective medicines to preserve normal renal function and to prevent or slow the progression of diabetic nephropathy.

Although diabetic nephropathy involves many renal cell types, mesangial activation by cytokines under hyperglycemic conditions plays an important role in the progression of diabetic nephropathy (2). The cytokine transforming growth factor- β 1 (TGF- β 1) is central to the profibrotic switch and activation of mesangial cell hypertrophy and matrix production and is upregulated in diabetic nephropathy (3). Previous interventions at the level of TGF- β 1 ameliorated several pathological symptoms of diabetic nephropathy (4), indicating reduction of hypertrophy and extracellular matrix (ECM) accumulation in the kidney may be a viable therapeutic avenue.

The transcription factor NFE2-related factor 2 (Nrf2) is an emerging therapeutic target for several diseases. Nrf2 regulates expression of numerous genes through antioxidant response elements in their promoters to neutralize free radicals and accelerate removal of environmental toxins (5). Using streptozotocin (STZ)-induced diabetic models, a protective role of Nrf2 against renal damage through mediation of free radicals was demonstrated (6). This may be also associated with the suppression of TGF β related genes including fibronectin, collagen IV and thrombospondin-1 (TSP-1), which too are known to contribute to the pathogenesis of diabetic nephropathy. In addition, recent work has shown that heparanase, the enzyme which destroys heparan sulfate, an important integral part of the glomerular basement membrane, may also contribute to the pathogenesis of diabetic nephropathy (7).

Treatment of type 2 diabetes with GLP-1 receptor agonists over the past decade has revealed a number of important attributes of this drug class besides their ability to improve glycemic control through increased insulinogenesis, decreased glucagon secretion, slowing of gastric emptying and the suppression of appetite and carbohydrate intake (8-10). We reported for the first time that exenatide, the first marketed drug in this class, induced a significant reduction in systolic blood pressure and plasma CRP concentrations. The latter observation was indicative of an anti-inflammatory effect. The systolic blood pressure lowering effect of exenatide, liraglutide and other drugs in this class has now been confirmed by other studies, including our own, in both type 2 and type 1 diabetes. In addition, the reduction in CRP concentrations has been followed by studies demonstrating

a rapid and comprehensive ROS suppressive and anti-inflammatory action of exenatide at the cellular and molecular level. Since hypertension and oxidative and inflammatory stress are major factors in the pathogenesis of diabetic nephropathy, we wondered whether exenatide and other drugs in this class could prevent or reverse albuminuria. This suspicion was strengthened further by the observation that exenatide suppresses the plasma concentrations of TGF β and also suppresses TGF β signal transduction by reducing the expression of SMAD3 and SMAD4. In addition, exenatide also enhances the expression of key anti-oxidant enzymes, NQO-1, GST-1P and HO-1, modulated by anti-oxidant response elements (ARE) which, in turn, are regulated by the Nrf-2/Keap-1 system. The action of this system has now been shown to be protective to the kidney in mouse models of experimental diabetes (11).

On the basis of the above, we hypothesized that exenatide and other drugs in this class reverse albuminuria. Data from a retrospective analysis on patients with type 2 diabetes from our center clearly show that treatment with GLP-1 receptor agonists (mainly exenatide and liraglutide) is associated with reductions in the magnitude of albuminuria in the entire group. In addition, there was a significant reversal of macroalbuminuria to micro- and normoalbuminuria and that of microalbuminuria to normoalbuminuria. In contrast, no such changes were observed in patients treated with other anti-diabetic drugs in spite of similar glycemic and blood pressure control.

Clearly, therefore, a prospectively randomized study needs to be set up to determine whether GLP-1RAs reduce the progression of albuminuria or reverse albuminuria. If indeed, this is shown to be true, we shall have an anti-diabetic drug class which for the first time will have an effect on the development of microangiopathy in addition to its role as an anti-hyperglycemic agent. In this proposal, we intend to investigate the hypothesis that treatment of with weekly exenatide reduces the rate of progression of albuminuria in patients with type 2 diabetes.

Preliminary data:

1- Effect of GLP-1 RA on evolution of albuminuria in type 2 diabetes: A retrospective study.

Among 466 patients with type 2 diabetes, 70.6 % (n=329) had normoalbuminuria, 24 % (n=112) had microalbuminuria and 5.1 % (n=24) had macroalbuminuria. Over a mean 3 year follow up, there was a reduction in UACR in the entire group by 21.1 ± 328 mg/g from a mean of 85.8 ± 374 mg/g to 65.1 ± 225 mg/g. In group A, UACR fell by 37 ± 193 mg/g (from 87 ± 250 mg/g to 49.8 ± 147 mg/g, $p < 0.0001$), while in group B, UACR increased by 6 ± 454 mg/g (from 81.1 ± 500 mg/g to 87 ± 302 mg/g, $p < 0.05$) ($p < 0.001$ between groups).

Since there was a significant difference in the reduction of HbA1c between groups A and B, we carried out a secondary analysis on UACR differences to adjust for the fall in HbA1c. UACR changes from baselines were first log transformed and difference between groups were tested with ANCOVA with changes in HbA1c used as a covariate. HbA1c adjusted log change in UACR in group A was -0.09 ± 0.49 and in group B was 0.08 ± 0.056 ($p = 0.007$, ANCOVA).

In the entire cohort (n=466), those with baseline normoalbuminuria (n=329), 88.7 % (n=292) remained normal, 10% (n=33) developed microalbuminuria and 1.2% (n=4) developed macroalbuminuria. Among those with baseline microalbuminuria (n = 112), 47.3% (n = 53) regressed to normal, 47.3 % (n =53) remained microalbuminuric, while 5.3 % (n=6) progressed to macroalbuminuria. Among those with baseline macroalbuminuria (n=24), 4% regressed to normal, and 50% regressed to microalbuminuria while 46 % remained macroalbuminuric.

The GLP-1RA users (group A; n =275) were followed up for a mean of 2.3 years.

[figure not shown]
- (a) Among those who had normoalbuminuria at baseline (n=183), 171 (93.4%) remained normal, 10 developed microalbuminuria (5.4%) and 2 developed macroalbuminuria (1%) as depicted in Figure 1. The mean UACR changed from 9.4 ± 7.1 mg/g to 18.1 ± 17.2 mg/g. The mean creatinine concentration changed from 0.98 ± 0.38 mg/dl to 1 ± 0.34 mg/dl. The eGFR decreased by 5.1 ± 18.4 ml/min from 95.7 ± 31.3 ml/min to 90.7 ± 30.2 ml/min. The mean HbA1c decreased by 0.7 ± 1.7 % from 7.9 ± 1.7 % to 7.2 ± 1.4 %.
- (b) Amongst 76 patients who had baseline microalbuminuria, 44 patients (57.8%) normalized while 32 (42.1%) remained microalbuminuric during follow up. No patient developed macroalbuminuria. The mean UACR fell by 57.7 ± 64.5 mg/g from 103.5 ± 68.8 mg/g to 45.8 ± 48.7 mg/g, a decrease of 42 ± 74 %. The mean creatinine changed from 1.04 ± 0.34 to 1.15 ± 0.42 mg/dl. The mean eGFR decreased by 8.6 ± 18 from 90.2 ± 36.9 ml/min (Table 2). Even in those who remained microalbuminuric, 22 had a reduction in UACR of 71.1 ± 54 mg/g from 155.4 ± 74 mg/g to 84.3 ± 55 mg/g. The mean HbA1c decreased by 0.8 ± 2.2 % from 8.4 ± 2 % to 7.6 ± 2 % in this group. The 10 patients who had no reduction in UACR had a significant increase in HbA1c from 9.2 ± 1.2 % to 9.7 ± 2.7 %.
- (c) Among the 15 patients who had macroalbuminuria at baseline, 1 normalized (6.6%), 8 became microalbuminuric (53.3%), and 6 remained macroalbuminuric (40%). The mean UACR fell by 500 ± 606 mg/g from 936 ± 579 mg/g to 436 ± 398 mg/g, a decrease of 40 ± 57 %. The mean creatinine increased from 1.37 ± 0.6 mg/dl to 1.47 ± 0.6 mg/dl. The eGFR decreased from 76.5 ± 36.5 ml/min to 70.1 ± 34.6 ml/min. The mean HbA1c decreased by 1 ± 1.2 % from 8.4 ± 1.8 % to 7.4 ± 1.6 %.

The GLP-1RA non-users (group B; n=191), were followed up for a mean period of 3.6 years.

- a) 146 patients had normo-albuminuria at baseline. Of these, 121 (82.8%) remained normal, 23 (15.7%) developed microalbuminuria and 2 developed macroalbuminuria (1.3%). The mean UACR increased by 20.6 ± 81 mg/g from 8.1 ± 6.9 mg/g to 28.7 ± 82.4 mg/g. The mean creatinine remained stable from 1 ± 0.36 mg/dl to 1.04 ± 0.39 mg/dl. The eGFR decreased from 89.1 ± 27.9 ml/min to 87.4 ± 29.5 ml/min. The mean HbA1c decreased by 0.4 ± 1.8 % from 7.5 ± 1.7 % to 7.1 ± 1.4 %.
- b) 36 patients had microalbuminuria at baseline. Of these, 9 normalized (25%), 21 remained microalbuminuric (58.3%) and 6 developed macroalbuminuria (16.6%). The mean UACR increased by 60 ± 201 mg/g from 85 ± 48 mg/g to 145 ± 199 mg/g, an increase of 105 ± 311 %. The mean creatinine changed from 1.06 ± 0.39 mg/dl to 1.2 ± 0.46 mg/dl. The eGFR decreased by 12.1 ± 15.8 ml/min from 85.3 ± 31.3 ml/min to 73.2 ± 26.7 ml/min. The mean HbA1c decreased by 0.5 ± 1.6 % from 7.8 ± 2.1 % to 7.3 ± 1.8 %.
- c) 9 patients had baseline macroalbuminuria. Of these, none normalized, 4 became microalbuminuric (44.4%), 5 remained macroalbuminuric (55.5%). The mean UACR

fell by 453 ± 2085 mg/g from 1248 ± 2075 mg/g to 795 ± 1111 mg/g, a decrease of $11 \pm 98\%$. The mean creatinine increased from 1.15 ± 0.5 mg/dl to 1.6 ± 0.59 mg/dl. The mean eGFR decreased by 30.3 ± 23.3 ml/min from 88.5 ± 47.9 ml/min to 58.2 ± 37.5 ml/min. The mean HbA1c decreased by $1.5 \pm 3.3\%$ from $9.2 \pm 2.9\%$ to $7.7 \pm 1.5\%$.

Figure 1 below compares the evolution of albuminuria per annum between groups A and B.

2- Effect of exenatide on Nrf-2/keap-1 system, expression of anti-oxidant enzymes and TGF β -1 in MNC. Twenty four obese type 2 diabetics taking insulin were randomized to receive either exenatide 10 μ g twice daily or placebo twice daily for 12 weeks. Fasting blood samples were obtained at baseline and 3, 6 and 12 weeks later. Exenatide treatment suppressed Keap-1 protein by $21 \pm 8\%$ and increased the mRNA expression of NQO-1, GST-1P and HO-1 by $51 \pm 15\%$, $42 \pm 10\%$ and $39 \pm 10\%$, with an increase in NQO-1 protein by $25 \pm 10\%$ ($p < 0.05$) in MNC. Exenatide also suppressed plasma TGF β 1 concentrations by $20 \pm 7\%$ and SMAD-3 expression in MNC by $28 \pm 8\%$ (Figure 2, $p < 0.05$).

[figure not shown]

Figure 2: Change in mRNA expression of Keap-1, activity of Nrf-2, expression of NQO-1 and SMAD-3 in MNC and plasma concentrations of TGF- β 1 following placebo and exenatide 10 μ g daily for 12 weeks in type 2 diabetic subjects. N=12 each, data are presented as mean \pm SE. (*: $P<0.05$ by RMANOVA (compared to baseline), #: $P<0.05$ by Two-way RMANOVA compared to control groups.

3.2 Include complete citations or references.

Response:

4.0 Study Design

4.1 Describe and explain the study design (e.g. case-control, cross-sectional, ethnographic, experimental, interventional, longitudinal, observational).

Response:

This is a single center, prospective, double blind, randomized, placebo –controlled in a parallel design study. The study will be conducted at the Diabetes – Endocrinology Center of Western New York under the direction of [name], M.D, [name], MD and [name], PhD.

Ninety (90) T2DM patients with micro- or macroalbuminuria (45 each) will be enrolled and randomized into 2 groups to receive placebo or exenatide-extended release treatments for 1 year. The study groups and treatment arms of this study are:

1. T2DM with Microalbuminuria: 30 patients on Exenatide extended release and 15 patients on placebo for 1 year
2. T2DM with Macroalbuminuria: 30 patients on Exenatide extended release and 15 patients on placebo for 1 year

5.0 Local Number of Subjects

5.1 *Indicate the total number of subjects that will be enrolled or records that will be reviewed locally.*

Response: 90

5.2 *If applicable, indicate how many subjects you expect to screen to reach your target sample (i.e. your screen failure rate).*

Response: All screened and qualified patients will be enrolled and randomized

5.3 *Justify the feasibility of recruiting the proposed number of eligible subjects within the anticipated recruitment period. For example, how many potential subjects do you have access to? What percentage of those potential subjects do you need to recruit?*

Response: The Diabetes and Endocrinology Center of WNY is the largest Diabetes center in the WNY area, seeing between 100 to 120 type 2 diabetes patients every week. Therefore, majority of recruited patients are our Kaleida Health and UBMD clinic patients. We will also recruit patients through advertisement, Buffalo Research Registry and researchmatch.org. These sources will suffice to recruit the needed number to subjects.

6.0 Inclusion and Exclusion Criteria

6.1 *Describe the criteria that define who will be **included** in your final study*

6.2 *sample.*

NOTE: This may be done in bullet point fashion.

Response:

Inclusion Criteria

- Type 2 Diabetes for at least 1 year.
- Microalbuminuria for at least 6 months (UACR: 30-300 mg/g)
- Macroalbuminuria for at least 6 months (UACR: >300 mg/g)
- HbA1c of $\leq 10\%$
- Ages 18-65 years (inclusive of ages 18 and 65)
- On ARBs/ACEi for at >3months

6.3 *Describe the criteria that define who will be **excluded** from your final study sample.*

NOTE: This may be done in bullet point fashion.

Response:

Exclusion Criteria

- Use of GLP-1 Receptor agonists or SGLT-2 inhibitors therapy in the last 3 months
- History or risk for pancreatitis (e.g., history of gallstones, alcohol abuse, and hypertriglyceridemia)
- Coronary event or procedure (myocardial infarction, unstable angina, coronary artery bypass, surgery or coronary angioplasty) in the previous 3 months
- Hepatic disease: Severe hepatic insufficiency and/or significant abnormal liver function defined as:
 1. Aspartate aminotransferase (AST) >3x upper limit of normal (ULN) and/or alanine aminotransferase (ALT) >3x ULN
 2. Total bilirubin >2.0 mg/dL (34.2 μ mol/L)
 3. Positive serologic evidence of current infectious liver disease including Hepatitis B viral antibody IGM, Hepatitis B surface antigen and Hepatitis C virus antibody
 4. Liver function tests more than 3 times the upper limit of normal
- *Renal impairment (serum eGFR <30 ml/min)*
- HIV
- Inability to give informed consent
- History of gastroparesis
- History of medullary thyroid carcinoma or MEN 2 syndrome
- Alcoholism
- Hypertriglyceridemia (>500 mg/dl).
- Any other life-threatening, non-cardiac disease
- Uncontrolled hypertension (BP > 160/100 mm of Hg)
- Congestive Heart Failure class III or IV
- Use of an investigational agent or therapeutic regimen within 30 days of study
- Participation in any other concurrent clinical trial
- Pregnant or breastfeeding patients or females of childbearing age not on 2 forms of acceptable contraceptives.

6.4 *Indicate specifically whether you will include any of the following special populations in your study using the checkboxes below.*

NOTE: Members of special populations may not be targeted for enrollment in your study unless you indicate this in your inclusion criteria.

Response: NA

- Adults unable to consent
- Individuals who are not yet adults (infants, children, teenagers)

- Pregnant women
- Prisoners

6.5 *Indicate whether you will include non-English speaking individuals in your study. Provide justification if you will exclude non-English speaking individuals.*

*In order to meet one of the primary ethical principles of equitable selection of subjects, non-English speaking individuals may **not** be routinely excluded from research as a matter of convenience.*

In cases where the research is of therapeutic intent or is designed to investigate areas that would necessarily require certain populations who may not speak English, the researcher is required to make efforts to recruit and include non-English speaking individuals. However, there are studies in which it would be reasonable to limit subjects to those who speak English. Some examples include pilot studies, small unfunded studies with validated instruments not available in other languages, studies with numerous questionnaires, and some non-therapeutic studies which offer no direct benefit.

Response: We have no non-English speaking patients in this population. We have patients that English is a second language, but they are able to read, write and understand it. This population is less than 10% of the total population.

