8.0 Eligibility Screening

8.1 *Describe screening procedures for determining subjects’ eligibility. Screening refers to determining if prospective participants meet inclusion and exclusion criteria.*

 *Include all relevant screening documents with your submission (e.g. screening protocol, script, questionnaire).*

Response:

After obtaining all necessary approval to conduct the study, study coordinator or investigators will conduct a prescreening phone conversation with referred or interested patients. Patients will then be schedule for a screening visit. Prospective participants will be asked to read and understand the consent and any questions they may have regarding the study will be answered. If the subject wants to participate in the study, they will be asked to sign the informed consent form. The subject’s medical history and current medications will be obtained as well as their blood pressure and vitals. Females of childbearing age will be tested for pregnancy and

asked to sign a commitment form to be on 2 forms of acceptable contraceptives for duration of study. A physical examination will also be done. Blood samples will be taken in order to evaluate HbA1c, CBC, CMP and liver and kidney functions and pregnancy status. Patients meeting all the inclusion and exclusion criteria based on all screening tests will be enrolled in the study.

- N/A:** There is no screening as part of this protocol.

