20.0 Withdrawal of Subjects

N/A: This study is not enrolling subjects. This section does not apply.

20.1 Describe anticipated circumstances under which subjects may be withdrawn from the research without their consent.

Response: The principal investigator of the study can remove a participant from the research study without their approval if for any reason he/she feels is appropriate, including

- i. Pregnancy
- ii. Developing conditions included in the exclusion criteria
- iii. Subjects decision to withdraw from the study
- iv. Severe side effects specific to study drugs
- v. Any medical condition that may place patient at risk of further complications
- vi. failure to take the medication as instructed, failure to keep your scheduled appointments,
- vii. cancellation of the study by the sponsor, or other administrative reasons.

20.2 Describe any procedures for orderly termination.

NOTE: Examples may include return of study drug, exit interview with clinician. Include whether additional follow up is recommended for safety reasons for physical or emotional health.

Response: If a subject withdraws from the research, the data collected to that point will be used toward the research finding. If applicable the subject will have to bring back any unused research drug and or device. If necessary, they will be asked to complete an end of study visit for their safety.

20.3 Describe procedures that will be followed when subjects withdraw from the research, including retention of already collected data, and partial withdrawal from procedures with continued data collection, as applicable.

Response: If a subject withdraws from the research, the data collected to that point will be used toward the research finding. If applicable the subject will have to bring back any unused research drug and or device. If necessary, they will be asked to complete an end of study visit for their safety.

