21.0 Risks to Subjects

21.1 List the reasonably foreseeable risks, discomforts, hazards, or inconveniences to the subjects related to their participation in the research. Consider physical, psychological, social, legal, and economic risks. Include a description of the probability, magnitude, duration, and reversibility of the risks.

NOTE: Breach of confidentiality is always a risk for identifiable subject data.

Response:

All subjects will be referred to exenatide and extended release exenatide labeling safety information and discussions of the potential side effects and the different warning and precautions will take place at the time of signing the informed consent and prior to treatment.

Potential side effects of GLP-1 agonist include hypotension, nausea, vomiting and other GI side effects. Patients will be provided guidance on potential side effects and how to properly manage and report it. The potential benefits including improved glycemia, improved BP, potential renal protection, improved quality of life (QOL) will most probably overcome the potential side effects.

Exenatide extended release caused rats to develop tumors of the thyroid gland. Some of these tumors were cancer. It is not known if Exenatide extended release will cause thyroid tumors or a type of thyroid cancer called medullary thyroid cancer in people. This will be discussed in details with all participating subjects. Exenatide is contraindicated in patients with a personal or family history of MTC and in patients with Multiple Endocrine Neoplasia syndrome type 2 (MEN 2).

Injection-site reactions: Serious injection-site reactions, with or without bumps (nodules), have happened in some people who use exenatide extended release. Some of these injection-site reactions have required surgical intervention. Report any injection site reactions including nodules to study investigators.

Severe allergic reaction (anaphylaxis) to study drugs or placebo ingredients or other interventions may accrue in rare cases. Epinephrine is the primary treatment for anaphylaxis with no absolute contraindication to its use. Our site and staff are trained and equipped to assist patients with such reactions. Severe conditions that are not satisfactorily managed in site will be transferred to the hospital emergency department for further assessment and help.

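### The exclusion list does not name a family history of medullary thyroid carcinoma, which the protocol's own risk section treats as a contraindication to exenatide

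*Combined protocol and SAP*

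**What the plan says.** Three parts of the combined protocol and SAP bear on this point.

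- **Eligibility.** The thyroid-related exclusion in Section 6.3 reads "History of medullary thyroid carcinoma or MEN 2 syndrome". It does not mention relatives.
- **Risk.** Section 21.1 reports that extended-release exenatide caused thyroid tumours in rats, some of them malignant, and that the risk in people is not known. It promises a discussion ("This will be discussed in details with all participating subjects") and then states: "Exenatide is contraindicated in patients with a personal or family history of MTC". The same sentence adds patients with MEN 2.
- **Entry.** Section 8.1 makes the listed criteria the test for enrolment: "Patients meeting all the inclusion and exclusion criteria based on all screening tests will be enrolled in the study". Section 5.2, answering a question about screen failures, says: "All screened and qualified patients will be enrolled and randomized".

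**The concern.** A contraindication stated in a protocol should appear in its exclusion list, because screening staff work from that list. Here the two differ on one group: patients with no MTC or MEN 2 of their own but with a relative who had MTC. Section 21.1 says they should not receive the drug, and Section 6.3 does not keep them out.

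What is at stake is patient safety. Allocation is 2:1 (60 exenatide, 30 placebo, Sections 4.1 and 17.2), so a patient admitted in this way has a 60/90 = 2/3 chance of exenatide, for a planned year. The visit procedures and schedule in Section 10 name no thyroid-specific test, so exclusion at entry is the natural control for this risk.

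**Working it through.** No arithmetic applies beyond the allocation fraction, and the plan gives no figure to reproduce. The check has two parts: compare the two statements, then look for any other rule that would exclude the patient.

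**1. The statements side by side**

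| Patient | Contraindicated (21.1) | Explicitly excluded (6.3) |
|---|---|---|
| Own history of MTC | Yes | Yes |
| MEN 2 | Yes | Yes |
| Family history of MTC only | Yes | No |

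The gap is confined to the third row.

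**2. Could the 6.3 wording already include family history?** It is unqualified, so a broad reading is possible. Three features of the text favour the narrow one:

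- Section 21.1 separates personal from family history, so the protocol itself treats them as different things.
- The other history items in 6.3, such as gastroparesis and gallstones, plainly concern the patient.
- Where 6.3 reaches beyond the patient's own history, it says so: the pancreatitis bullet covers risk as well as history.

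**3. Does any other rule exclude this patient?**

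- *Remaining bullets in 6.3.* The nearest catch-all is "Any other life-threatening, non-cardiac disease". A relative's cancer is not a disease of the patient, so it does not apply.
- *Screening, 8.1.* The subject's "medical history and current medications will be obtained". Family history is not mentioned there or in the visit schedule in Section 10.2. A history-taker may ask, but no text requires it.
- *Withdrawal, 20.1.* One listed reason is "Developing conditions included in the exclusion criteria". This points back to the same list and inherits its gap. The investigator may also remove a participant for any reason thought appropriate, but that is a discretion and it acts after enrolment.
- *Risk discussion, 21.1.* Labelling information and warnings are covered at consent and before treatment. This may well bring a family history to light, but nothing says that disclosure leads to exclusion.
- *Drug use, 31.3.* The statement that exenatide will be used within its indication answers a question about the IND holder. It names no contraindication and sets no entry rule.

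**4. How likely is it that the history is already known?** Recruitment extends to Facebook, Craigslist and registries (Section 9). Section 16.1 says the team will not access medical information of people its own clinic providers do not serve. For those recruits, a family history is likely to surface only if someone asks.

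**Result.** No eligibility rule in the documents requires a patient with only a family history of MTC to be excluded.

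**The case against.** The strongest reply is that this is an omission and not a conflict. Nothing in 6.3 invites such patients in. Section 21.1 belongs to the same protocol, and an investigator who follows the whole document would not dose someone it describes as contraindicated. Several steps come before the first dose: consent, a medical history, a physical examination and a discussion of the labelling and the thyroid risk. All would have to miss the history before harm could follow. The telephone screening form mentioned in Section 16.1 is not in the documents, and the consent pages were removed from this file. Either may already ask about family history. Section 5.2 answers a question about screen failures and should not be read as an order to randomise despite a known contraindication. Finally, such patients are few, the human tumour risk is unknown, and a cheap fix is not evidence of harm.

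Much of this stands. The practical risk is small, the unseen forms may reduce it further, and Section 5.2 adds little to Section 8.1. The point does not depend on whether the mismatch is called a contradiction or an omission. What does not stand is that these steps close the gap. None of them is an eligibility rule, and a question on a form or a paragraph in a consent document would not change what 6.3 says. If 6.3 is merely ambiguous about a contraindication, that too is a reason to reword it.

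**Conclusion.** The concern holds. Applied in its ordinary sense, the exclusion criterion would admit a patient for whom the protocol itself says the study drug is contraindicated. That makes the criterion wrong as written, and not just short on detail.

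The number of patients affected cannot be estimated from the documents. It is probably very small and may be zero in a trial of 90. The conclusion assumes that the 6.3 wording means the patient's own history, which is the more natural reading but not the only one, and that entry is decided by the listed criteria, as Section 8.1 says. It does not assume that staff would in fact miss such a patient. The change should be made on safety grounds. It has no bearing on the validity of the randomised comparison.

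**What to change.** Reword the bullet in Section 6.3 to: *Personal or family history of medullary thyroid carcinoma, or MEN 2 syndrome*. This brings it into line with Section 21.1. Add family history of MTC to the screening history in Section 8.1, and confirm that the telephone screening form asks about it if it does not already. Because the withdrawal reason in Section 20.1 refers back to the exclusion list, it will follow the new wording without further editing.

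The cost is one line in the criteria and one screening question, with possibly a very rare extra screen failure. Sample size, power and analysis do not change. If staff already apply the broader reading, the amendment only records their practice.
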